5. RESEARCH DESIGN

For each research question, briefly describe why the research design proposed will answer each research question(s). State whether the proposed evaluation is a descriptive or impact evaluation and justify why the proposed research design is best suited to answer the research question(s).

Research Question	Design	Justification
I1	Implementation: Ongoing monitoring of the number of services offered and provided as intended.	Ongoing monitoring of service data will help to ensure that services are being offered and provided in alignment with the program design. Monitoring of this data is beneficial, such that we will have more confidence in the results of the study.
I2	Implementation: Ongoing monitoring of the level of Fresno Fatherhood curriculum and services offered to and completed by participants.	Ongoing monitoring of service data and program participation completion rates will help to ensure that services are being offered and completed by participants as intended. Monitoring of this data is beneficial, such that we will have more confidence in the hypothesized results of the study.
I3	We expect that the CQI Team will carry out the steps in the CQI Plan during each program year.	Incorporating a CQI process will allow the program to identify problems, solutions, and implementation interventions with respect to meeting specific enrollment and completion targets throughout program implementation. Further, the CQI process will also allow the CQI team to test the

		effectiveness of interventions. This process will help the program produce more robust results for the program and the study.
R1	Descriptive: Pre to post assessment will examine the association of Fresno Fatherhood program participation on healthy parenting attitudes/beliefs/expectations immediately following program completion.	Healthy change reported by participants in their parenting attitudes/beliefs/expectations from pre to post assessment estimates the maximum amount of benefit that can be attributed to Fresno Fatherhood services in the absence of a counterfactual.
R2	Descriptive: Pre to follow-up assessment will examine the association of Fresno Fatherhood program on healthy parenting behaviors one year after program enrollment.	Healthy change reported by participants in their parenting behaviors from pre to follow-up assessment estimates the maximum amount of benefit that can be attributed to Fresno Fatherhood services in the absence of a counterfactual.
R3	Descriptive: Pre to follow-up assessment will examine the association of Fresno Fatherhood program on healthy co-parenting behaviors one year after program enrollment.	Healthy change reported by participants in their co-parenting behaviors from pre to follow-up assessment estimates the maximum amount of benefit that can be attributed to Fresno Fatherhood services in the absence of a counterfactual.
R4	Descriptive: Pre to post assessment will examine the association of Fresno Fatherhood program on healthy employment attitudes/beliefs/expectations immediately following program completion.	Healthy change reported by participants in their employment attitudes/beliefs/expectations from pre to post assessment estimates the maximum amount of benefit that can be attributed to Fresno Fatherhood services in the absence of a counterfactual.
R5	Descriptive: Pre to follow-up assessment will examine the association of Fresno Fatherhood program on healthy employment behaviors one year after program enrollment.	Healthy change reported by participants in their employment behaviors from pre to follow-up assessment estimates the maximum amount of benefit that can be attributed to Fresno Fatherhood services in the absence of a counterfactual.
R6	Descriptive: Pre to post assessment will examine the association of Fresno Fatherhood program on healthy financial attitudes/beliefs/expectations	Healthy change reported by participants in their financial attitudes/beliefs/expectations from pre to post assessment estimates the maximum amount of benefit that can be attributed to

	immediately following program completion.	Fresno Fatherhood services in the absence of a counterfactual.
R7	Descriptive: Pre to follow-up assessment will examine the association of Fresno Fatherhood program on healthy financial behaviors one year after program enrollment.	Healthy change reported by participants in their financial behaviors from pre to follow-up assessment estimates the maximum amount of benefit that can be attributed to Fresno Fatherhood services in the absence of a counterfactual.

* you may add rows by hitting the tab button, or right click and select insert row below

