1.2. OUTCOME RESEARCH QUESTIONS

For each outcome research question listed above, whether a descriptive or impact design, summarize the inputs (e.g., program components, program supports, implementation features, etc.), target population (e.g., the population for which the effect will be estimated) and the outcomes (e.g., child well-being, father-child engagement, etc.) that will be examined to answer the research question(s). Comparisons for descriptive evaluations may reflect circumstances before the grant, pre-treatment, or pre-determined benchmark from other studies with similar interventions.

Research Question Number Should correspond to the number indicated in Table 1.1 above	Intervention Program component or set of activities that the evaluation will test or examine	Target Population Population for which the effect of the treatment will be estimated	Comparison What the intervention will be compared to (e.g., pre-intervention for descriptive designs)	Outcome Changes that are expected to occur as a result of the intervention	Confirmatory or Exploratory? Confirmatory: those upon which conclusions will be drawn Exploratory: those that may provide additional suggestive evidence
R1	Interventions to be tested are the combination of the curriculum and services provided: 24/7 Dad curriculum,	Community fathers (ages 18 and older), who have children ages 24 and younger and reside in communities	Pre-intervention responses will be compared with responses collected immediately following program completion	We expect that program participants will experience a significant increase in healthy parenting attitudes/beliefs/expectations after completing the Fresno Fatherhood program.	Exploratory

	Job Readiness and Post-Employment support	with high rates of poverty.	(post-intervention).		
R2	Interventions to be tested are the combination of the curriculum and services provided: 24/7 Dad curriculum, Job Readiness and Post-Employment support	Community fathers (ages 18 and older), who have children ages 24 and younger and reside in communities with high rates of poverty.	Pre-intervention responses will be compared with responses collected 1-year post-enrollment (follow up).	We expect that program participants will experience a significant increase in healthy parenting behaviors one year after program participation.	Exploratory

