8. SAMPLE

8.1. TARGET POPULATION(S)

For each target population identified in Section 1.2, please describe the target population(s), and explicitly state whether the population(s) differs from those who will be broadly served by the grant. Describe how the target population will be identified. Explicitly state the unit of analysis (e.g., non-residential father, unmarried couple).

Description of Target Population	How is the population different from those who will be broadly served by the grant?	How will the target population be identified?	Unit of Analysis
Target population is community fathers (ages 18 and older), who have children ages 24 and younger and reside in communities with high rates of poverty.	No difference, all program participants will be study participants.	The sample will be identified and recruited by community partner referrals and program staff.	Community adult fathers

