9.3. METHODS OF DATA COLLECTION

If the evaluation will collect multiple waves of data, describe the timing of these waves below. When describing follow-up periods, specify whether the follow-up period will be post-baseline, post-random assignment, or post-program completion.

Wave of Data Collection (e.g., baseline, short-term follow-up, long-term follow-up)	Timing of Data Collection
Baseline	Collected immediately following informed consent and enrollment – during the orientation session or first workshop
Post-Test	Collected after the completion of core curriculum programming -during the last workshop session – approximately 4 weeks after enrollment.
1 year Follow-up (post-baseline)	Collected approximately one year after program enrollment/ baseline. Participants who did not complete the program will still be eligible for a follow-up survey as long as they consented to be in the study and took a baseline survey.

For each measure, describe how data will be collected detailing which data collection measures will be collected by which persons, and at what point in the programming or at what follow-up point.

Measure	Timing of Data Collection (baseline, wave of data collection)	Method of Data Collection	Who Is Responsible for Data Collection?	Impact Evaluations Only: Will Methods or Collection Procedures Differ by Study Group?	Administrative Data Only: Will data access require data sharing agreement?
Online Local Evaluation (OLLE) Baseline Survey	Baseline	Participant self-enters survey using online Qualtrics data collection platform	Case Manager and/or facilitator will proctor data collection and assist participants as necessary	N/A	N/A
nFORM Community Fathers Entrance Survey	Baseline	Participant self-enters survey using online nFORM data collection platform	Case Manager and/or facilitator will proctor data collection and assist participants as necessary	N/A	N/A
OLLE Post-Test Survey	Post-Test (approx. 4 weeks after enrollment)	Participant self-enters survey using online Qualtrics data collection platform	Case Manager and/or facilitator will proctor data collection and assist participants as necessary	N/A	N/A
nFORM Community Fathers Exit Survey	Post-Test (approx. 4 weeks after enrollment)	Participant self-enters survey using online nFORM data collection platform	Case Manager and/or facilitator will proctor data collection and assist participants as necessary	N/A	N/A

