#### **Analytic approach**

The main goal of this descriptive study is to assess pre-to-post change scores in the attitudinal outcomes listed above, and assess pre-to-one-year follow-up change scores in the behavioral outcomes listed above among program participants before and after primary workshops. We will use paired sample t-tests to assess the magnitude and significance of changes among program participants in the analytic sample for each outcome. For binary economic stability outcomes, we will descriptively report the percent of participants who opened a checking or savings account 1 year after enrollment, compared to the percent who had opened these accounts before the program. For binary employment outcomes, we will descriptively report the percent of participants who did not have a resume 1 year after enrollment, compared to the percent who did not have a resume before the program. We will adjust our p-values for multiple hypothesis testing and report the adjusted p-values in the appendix of the final report.

For the implementation analysis, program fidelity will be descriptively reported by the percentage of enrolled participants who receive: 1) any primary workshops, 2) employment supports, 3) substantive service contacts, 4) referrals. The program aims to provide all participants each of these four program components, so the percentage of participants who receive each of these will be compared to the 100% benchmark. Number of substantive service contacts per participant will also be compared to the benchmark of 8 SSCs set by OFA for FIRE grantees.

Exploratory analysis will examine how dosage varies by workshop characteristics (e.g., timing and length of sessions) and participant characteristics (e.g., age, employment status, relationship status).

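### Protocol Section 5 calls pre-post change the maximum attributable benefit, an upper bound that a single-group design does not supply for the outcome questions other than R5

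*Protocol*

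**What the plan says.** Protocol Section 5 (Research Design) gives each outcome question a design and a justification. The justification for all seven is that healthy change reported by participants "estimates the maximum amount of benefit that can be attributed to Fresno Fatherhood services in the absence of a counterfactual". Only the outcome and the time window differ from row to row; no other justification is offered.

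The same rows label the design descriptive and speak of association. For R2, for example: "Pre to follow-up assessment will examine the association of Fresno Fatherhood program on healthy parenting behaviors one year after program enrollment".

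The rest of the plan confirms that there is one group and no external comparator:

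- Protocol Section 1.2 compares each participant's later responses with his own pre-program responses.
- On how the target population differs from those served by the grant, Protocol Section 8.1 answers: "No difference, all program participants will be study participants".
- Under Protocol Section 9.3 the attitude outcomes (R1, R4, R6) are measured about 4 weeks after enrollment. The behavioral outcomes (R2, R3, R5, R7) are measured at follow-up: "Collected approximately one year after program enrollment/ baseline".
- The SAP, under Analytic approach, states: "We will use paired sample t-tests to assess the magnitude and significance of changes among program participants in the analytic sample for each outcome". The binary outcomes (R5 and R7) are reported as percentages before and after.

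The SAP does not repeat the claim about a maximum. Neither document says what would have happened to these outcomes without the program.

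**The concern.** A maximum attributable benefit is a causal bound: the true effect is said to be no larger than the change observed. A before-after comparison in one group does not provide that. Observed change mixes the program effect with whatever else moved over the interval, and with differences in how, and from whom, the two measurements were taken. If those other components are negative on balance, the observed change is smaller than the effect and is not a maximum. If they are positive on balance, it overstates the effect.

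What is at stake is the claim the final report may make. Section 5 is where the plan explains why the design answers its questions, and the program summary says the findings should help providers replicate effective practice. A report that carried the sentence forward would present a bound that the data cannot support. No test, p-value or sample size is affected.

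**Working it through.** The plan gives no effect size, standard deviation or trend for these outcomes, so there is no figure to reproduce. The check is of the logic, with labelled assumptions for scale.

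**Condition for an upper bound.** Write

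observed change = E + U + M

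where E is the program effect, U the change that would have occurred without the program, and M the net measurement and selection difference. Then observed change ≥ E if and only if U + M ≥ 0. Only the net sum matters; each influence need not be favorable.

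**Can the documents establish U + M ≥ 0?**

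- *R2 and R3, one year.* The program summary expects many participants to be non-custodial or justice-involved. Contact and co-parenting could worsen over a year for reasons unrelated to the program. The SAP's missing-data section scores parenting behavior as 1 (never) for a father who has not seen his child in the past month, so lost contact lowers R2 directly. This example relies on that rule; the SAP's measure table instead lists recent contact as a sample condition for the same outcome.
- *R7, one year.* Protocol Section 9.1 asks about having an account, which can be lost. The SAP measure table speaks of having opened one. If that means ever opened, the status cannot be lost, so U ≥ 0.
- *R1, R4 and R6, about 4 weeks.* A year of worsening circumstances cannot apply. Protocol Section 9.4 limits the post-test to completers present at the last session, and self-ratings may shift after instruction. The documents give no evidence on the sign of either influence.
- *Mode, one-year outcomes.* Baseline is self-entered with staff proctoring; follow-up is online or by phone interview (Section 9.3). M could have either sign.

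**Illustration on the 1-5 scale** (assumed E = +0.3, M = 0; observed = 0.3 + U):

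| Untreated change U | Observed change | At or above E? |
|---|---|---|
| -0.4 | -0.1 | no |
| -0.2 | +0.1 | no |
| 0 | +0.3 | yes |
| +0.2 | +0.5 | yes |
| +0.4 | +0.7 | yes |

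**Illustration for R7 as currently having an account** (assumed 60% at baseline, 65% at follow-up). Observed change = 65 - 60 = +5 points. Effect = 65 minus the untreated follow-up percentage:

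| Untreated follow-up | Effect (points) |
|---|---|
| 50% | +15 |
| 55% | +10 |
| 60% | +5 |
| 65% | 0 |
| 70% | -5 |

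The same observed +5 is consistent with effects above and below it.

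**R5 exception.** The SAP measure table restricts this outcome to fathers without a resume at entry, so the baseline proportion with a resume is 0. Let p1 be the follow-up proportion with a resume and p0 the proportion had the same fathers not had the program. Observed change = p1 - 0 = p1, and effect = p1 - p0. Because p0 ≥ 0, p1 ≥ p1 - p0 always. With assumed p1 = 0.40 and p0 = 0.30, observed change is 0.40 and the effect is 0.10. Among accurately reporting respondents the bound holds, but it comes from the sample restriction, which Protocol Sections 5 and 9.1 do not mention.

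**The case against.** The strongest defense is that the sentence is meant as caution. The rows say descriptive and association, and they acknowledge that there is no counterfactual. Section 1.2 marks all seven questions exploratory. On that reading, the sentence means only that no more than the observed change may be credited to the program. The SAP speaks only of change scores and builds no bounding analysis or decision rule on the word maximum.

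Part of this stands. The SAP needs no correction on this point, and the paired analysis is suitable for describing within-group change. The hedges still do not supply the missing assumption: lacking a counterfactual is the reason no bound can be claimed. Nor is the exploratory label clean, since Protocol Section 3 calls the logic-model outcomes confirmatory.

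Three stronger readings are tempting and should be resisted:

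- A reader might infer that the bound fails for all seven questions. R5, as restricted in the SAP, is an exception, and R7 would be one for untreated change if it means ever having opened an account.
- A reader might infer that a null or negative change would be taken as proof of no benefit. Neither document contains such a rule, and the sentence concerns healthy change only.
- A reader might infer that the observed changes will understate the effect. The documents do not determine the direction; the error could equally be overstatement.

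**Conclusion.** The claim of a maximum is wrong as written for R1, R2, R3, R4 and R6, and for R7 if it measures currently having an account. It requires a non-negative net of trend, measurement and selection, which the documents neither state nor support. The case is strongest for R2, R3 and R7 on that reading. For R1, R4 and R6 the bound is equally unsupported, but nothing shows which way the error would run. For R5 the bound holds among accurately reporting respondents, because of the SAP's sample restriction and not because of the pre-post design.

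The error equals the net non-program change, which this study cannot measure. The numerical values above are assumptions that show how the sign can turn; they are not estimates for this program. The consequence is confined to interpretation.

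**What to change.** In the R1, R2, R3, R4, R6 and R7 rows of Protocol Section 5, replace the clause about maximum benefit with: *estimates the observed change among participants, which may overstate or understate the program's contribution because there is no counterfactual*.

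For R7, also settle whether the measure is currently having an account or ever having opened one. If the latter, untreated change cannot be negative and the row can say so.

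In the R5 row, state that observed change may overstate the program's contribution, and that any upper bound rests on the SAP's restriction to fathers without a resume at entry and on accurate reporting.

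In the final report, describe results as within-group change and not as a maximum or an attributable benefit.

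The cost is a wording amendment and a slightly weaker permitted claim. No data collection, test or sample size changes.

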6. ONGOING GRANTEE AND LOCAL EVALUATOR COORDINATION

Describe how the grantee and local evaluator collaboratively worked together to identify the research question(s) and research design to ensure its feasibility and relevance. Describe how the grantee and local evaluator will continue to work together throughout the evaluation to proactively address unforeseen challenges as they arise and ensure the rigor and relevance of the evaluation and its findings. Describe how the grantee and local evaluator will coordinate dissemination efforts. Describe how these processes will occur while maintaining the independence of the evaluation.

The basis for ongoing coordination between FAWIC (the grantee) and MER (the local evaluator) is regular communication, by way of recurring meetings and daily interactions with embedded staff. Throughout the original proposal process, and now during the evaluation planning phase, MER worked in consort with FAWIC to design a study with research questions that are appropriate to the intervention. MER guides the process, given our experience designing and running evaluations, and FAWIC provides expertise on their community, target population, and program/curricula specifics.

Recurring meetings will include a bi-weekly project CQI Team meeting. Under the leadership of the Data Manager and Lead MER Evaluator, the CQI Team reviews data from the nFORM and local evaluation systems to identify and mitigate implementation or data issues, and closely examine trends and accomplishments. This team includes FAWIC organizational and project leadership, the MER Evaluation team, and front-line staff representatives (e.g., Case Managers).

In addition to CQI Team meetings, overall project team meetings occur monthly (at a minimum), with project leaders across MER and FAWIC in attendance, to ensure the partnership remains strong and that coordination across organizations is on track. This recurring, ongoing meeting structure is conducive to close coordination, ensuring that challenges can be quickly addressed, and promising strategies can be efficiently maximized.

One of the key components of this coordination effort is the CQI Data Manager, who is an employee of FAWIC. The CQI Data Manager functions to bridge the gap between MER and FAWIC. They will interact with FAWIC staff daily while completing their job duties and play a leadership role in the recurring meetings outlined above. See *Section II.D. above for more details about this role and others*. Both the meetings and the roles outlined above will continue throughout the entire project period, providing opportunities to ensure the rigor and relevance of the evaluation

and its findings, and to discuss and coordinate dissemination efforts (which will also be shared across MER and FAWIC).

MER has experience operating prior descriptive evaluations using this exact process.

Clearly outlining roles and responsibilities maintains the independence of the evaluation. That is, the evaluation team helps identify and illuminate areas of concern or improvement (for the program and the evaluation), but the program staff have responsibility for implementing improvements and providing direct services to participants. In this way, FAWIC and MER acknowledge our shared interest in and responsibility for a well-executed project and evaluation, but that MER is also an independent and external organization with a high level of integrity and is not responsible for nor invested in the specific outcomes of the program. This allows for close coordination without allowing for co-dependence, or for personal interests to influence evaluation findings.

